7.2 Biological Sample Submissions

1. Bone marrow and peripheral blood samples should be submitted as outlined in Section 10 of E3A06 for correlative studies and/or banking per patient consent. Kits are being provided for the collection and shipment of the samples, please refer to Section 10 and Appendices III and IV for instructions.

NOTE: Institutions outside of the United States and Canada must confer with the receiving laboratory and the ECOG-ACRIN Operations Office - Boston regarding logistics for submission of fresh samples.

Rev. 7/14

NOTE: It is required that biological sample submissions be logged into the ECOG-ACRIN Sample Tracking System (STS) (see Section 10.5) for purposes of monitoring compliance.

Rev. 2/12

NOTE: An informed consent must be signed prior to the submission of any samples for laboratory studies and/or banking. Samples for the optional laboratory studies and/or banking should be submitted only from patients who have given written consent for the use of their samples for these purposes.

Rev. 7/14

Biological Materials ^{3,4}		Pre-Registration ¹	At Study Discontinuation or Progression ²	Ship To:
From Patients Who Answer "YES" to "I agree to participate in the laboratory research studies that are being done as part of this clinical trial."				
Peripheral Blood	Two (2) ACD tubes (yellow top), 14mL	X	X	Mayo Clinic Myeloma Reference Laboratory
	Four (4) 10mL Green Top tubes (sodium heparin)	X	X	Yale University
Bone Marrow Core Biopsy	Five (5) Unstained Slides	X	X	Mayo Clinic Myeloma Reference Laboratory
	Snap Frozen	X	X	University of Arkansas
[Deleted in Addendum #7]				
Bone Marrow Aspirate	One (1) ACD tube (yellow top), 7mL	X	X	Mayo Clinic Myeloma Reference Laboratory
	5-10mL Sodium Heparin (green top tube)	X	X	Yale University
	EDTA tube (purple top), 10-20mL	X	X	University of Arkansas
From Patients Who Answer "YES" to "I agree to provide additional blood for research."				
Peripheral Blood	One (1) SST tube (red top), 5-7mL	X	X	Mayo Clinic Myeloma Reference Laboratory

Rev. 2/12
7/14

1. Prior to treatment.

Rev. 7/14

2. Whichever comes first. Biopsies performed at time of suspected progression are requested.

Rev. 2/12

3. Submissions are optional based on patient consent to the correlative studies and/or banking as outlined in Section 10.

4. Kits are available for the collection and shipment of the samples. See Section 10.3.

8. Drug Formulation and Procurement

8.1 Lenalidomide (NSC 703813), (IND)

Rev. 8/11

NOTE: Before lenalidomide is dispensed, patients must 1) have a negative pregnancy test (if applicable) and 2) be counseled by a trained counselor. Pharmacists may be trained counselors (see Lenalidomide Counselor Program Site Counselor Identification Form in the protocol). The counseling requirements for investigational-use lenalidomide are separate from the RevAssist program. Only a 28-day supply may be dispensed to a patient at one time.

8.1.1 Other names

Revlimid® (formerly Revimid®), CDC-501, CC-5013

8.1.2 Classification

Immunomodulatory drug.

Rev. 8/11

8.1.3 Mode of Action

Lenalidomide, a thalidomide analog, is an immunomodulatory agent with a spectrum of activity that is still under investigation. Some of its effects include inhibition of inflammation, inhibition of angiogenesis, inhibition of hematopoietic tumor cell proliferation, modulation of stem cell differentiation and upregulating responses of T cells and NK cells.

Rev. 8/11, 12/13

8.1.4 How Supplied

Celgene supplies and CTEP, NCI, DCTD distributes lenalidomide 5 mg (size 2) and 25 mg (size 0) hard gelatin capsules in tamper-evident, child-resistant, opaque, high density polyethylene (HDPE) bottles with HDPE caps. Bottles contain 100 capsules per container.

The capsules also contain anhydrous lactose, microcrystalline cellulose, croscarmellose sodium, and magnesium stearate.

Rev. 8/11

8.1.5 Storage and Stability

Storage: The capsules should be stored at room temperature (15-30°C) away from moisture and direct sunlight.

Stability: Refer to the package labeling for expiration date. Lenalidomide stability is adequate for at least 28 days after transferring to a pharmacy vial.

NOTE: Per FDA guidelines for prevention of pregnancy that only one month supply of lenalidomide may be dispensed to the patient at one time.

Rev. 8/11, 12/13

Dispensing

Only a 28-day supply may be dispensed at one time. Sites may not mail lenalidomide to patients.

8.1.6 Dose Specifics

For Arm A patients, lenalidomide is initiated on Day 1 of Cycle 1 at a dose of 25 mg orally and will be taken days 1-21 for each 28 day cycle.

Only enough lenalidomide for one cycle of therapy will be supplied to the patient each cycle.

Lenalidomide capsules should be swallowed whole, and should not be broken, chewed, or opened.

If a dose of lenalidomide is missed, it should be taken as soon as possible on the same day. If it is missed for the entire day, it should not be made up.

Patients who take more than the prescribed dose of lenalidomide should be instructed to seek emergency medical care if needed and contact study staff immediately.

Rev. 8/11

8.1.7 Route of Administration

Take lenalidomide by mouth with or without food. Do not crush, chew or open capsules.

Rev. 8/11

8.1.8 Patient Care Implications and Counseling

Risks Associated with Pregnancy

Lenalidomide is structurally related to thalidomide. Thalidomide is a known human teratogenic active substance that causes severe life-threatening birth defects. An embryofetal development study in animals indicates that lenalidomide produced malformations in the offspring of female monkeys who received the drug during pregnancy. The teratogenic effect of lenalidomide in humans cannot be ruled out. Therefore, a risk minimization plan to prevent pregnancy must be observed.

Definition of female of childbearing potential (FCBP)

This protocol defines a female of childbearing potential as a sexually mature woman who: 1) has not undergone a hysterectomy or bilateral oophorectomy or 2) has not been naturally postmenopausal (amenorrhea following cancer therapy does not rule out childbearing potential) for at least 24 consecutive months (i.e., has had menses at any time in the preceding 24 consecutive months).

Before starting study drug:

Female Subjects:

- FCBP must have two negative pregnancy tests (minimum sensitivity of 25 mIU/mL) prior to starting study drug. The first pregnancy test must be performed within 10-14 days prior to the start of study drug and the second pregnancy test must be performed within 24 hours prior to the start of study drug. The subject may not receive study drug until the Investigator has verified that the results of these pregnancy tests are negative.

Male Subjects:

- Must agree to use a latex condom during sexual contact with females of childbearing potential while participating in the study and for at least 28 days following discontinuation from the study even if he has undergone a successful vasectomy.

All Subjects:

- Only enough lenalidomide for one cycle of therapy may be dispensed with each cycle of therapy.
- If pregnancy or a positive pregnancy test does occur in a study subject or the partner of a male study subject during study participation, lenalidomide must be immediately discontinued.

Counseling

- In investigational studies where lenalidomide is supplied by the NCI, patients will be counseled by a qualified healthcare professional (including but not limited to, nurses, pharmacists and physicians). Two healthcare professionals at each site will be trained by Celgene in requirements specific to counseling of subjects (investigators cannot counsel patients as part of this requirement). Refer to specific protocol sections for more information about training requirements.
- Once trained, these healthcare staff will counsel subjects prior to medication being dispensed to ensure that the subject has complied with all requirements including use of birth control and pregnancy testing (FCBP) and that the subject understands the risks associated with lenalidomide. This step will be documented with a completed Lenalidomide Education and Counseling Guidance Document ([Appendix VII](#)) and no drug will be dispensed until this step occurs. Counseling includes verification with the patient that required pregnancy testing was performed and results were negative. A Lenalidomide Information Sheet ([Appendix VIII](#)) will be supplied with each medication dispense.

8.1.9 Potential Drug Interactions

Periodic monitoring of digoxin levels is recommended during coadministration with lenalidomide. Digoxin levels were slightly higher when digoxin was administered with lenalidomide in a clinical study. There was no effect on lenalidomide pharmacokinetics.

Warfarin and lenalidomide may be co-administered without additional monitoring. No pharmacokinetic or pharmacodynamic interactions were observed between lenalidomide and warfarin.

Nonclinical in vitro metabolism studies suggest that lenalidomide is not likely to result in metabolic drug interactions in humans. In vitro, lenalidomide did not significantly inhibit marker enzyme activities for CYP1A2, CYP2C9, CYP2C19, CYP2D6, CYP2E1, or CYP3A4. In rats, no induction of any CYP450 enzymes was observed.

Administration of lenalidomide in monkeys showed no effects on the activities of CYP1A, CYP2B, CYP2C, CYP2E, CYP3A, or CYP4A.

Rev. 7/13

8.1.10 Availability

Available as a 5 mg and 25 mg hard gelatin capsule.

Drug Ordering: Maintenance of NCI drug accountability records is required. Lenalidomide may be requested by the Principal Investigator (or their authorized designees) at each participating institution. Pharmaceutical Management Branch (PMB) policy requires that drug be shipped directly to the institution where the patient is to be treated. PMB does not permit the transfer of agents between institutions (unless prior approval from PMB is obtained - see general information).

Rev. 12/13

NCI SUPPLIED AGENT(S) - GENERAL INFORMATION

Active CTEP-registered investigators and investigator-designated shipping designees and ordering designees can submit agent requests through the PMB Online Agent Ordering Processing (OAOP) application (<http://eapps-ctep.nci.nih.gov/OAOP/pages/login.jsp>). Access to OAOP requires the establishment of a CTEP Identity and Access Management (IAM) account (<https://eapps-ctep.nci.nih.gov/iam/>) and the maintenance of an “active” account status and a “current” password.

For questions about drug orders, transfers, returns, or accountability, call [contact] Monday through Friday between 8:30 am and 4:30 pm (ET) or email [contact] anytime.

Drug Accountability: The investigator, or a responsible party designated by the investigator, must maintain a careful record of the receipt, disposition, and return of all drugs received from the PMB using the NCI Investigational Agent Accountability Record available on the NCI home page (<http://ctep.cancer.gov>) or by calling the PMB at [contact].

8.1.11 Side Effects

See CAEPR (Section [5.3](#))

8.1.12 Nursing/ Patient Implications

Please refer to [Appendix VI](#): Risk Associated with Pregnancy and [Appendix VII](#): Education and Counseling Guidance Document.

1. Ensure women of childbearing age are not pregnant and sexually active women and men are abstaining or are using an effective form of contraception while taking lenalidomide.
2. Caution patient not to drive or use hazardous machinery until the potential sedative effects of the drug are known in the patient.
3. Caution patient to report leg swelling or shortness of breath, because of the risk of thrombosis/embolism

4. Counsel patient to report abnormal sensations in hands or feet, such as decreased sensation or dysesthesia. Paresthesias are often noted early before neuropathy develops.
5. Advise patient to immediately report rashes or fever.
6. Advise patient to take dose at the same time each day.

9.1 Introduction

This revised statistical considerations section reflects observed accrual and updated results of the Spanish SMM trial at ASH 2014 (Mateos et al. Blood 2014).

As of the end of June 2015, 93 patients have enrolled over the 26 months since accrual began on the Phase III study (Feb 2013). The accrual rate over this time was approximately 3.5 patients per month, which approximates 50% of the anticipated accrual rate (7 patients per month). Accrual over the last 6 months has averaged 4.5 patients per month. Following the recommendation of the Data Safety Monitoring Committee, the anticipated accrual rate is revised in addendum #11 to reflect the current actual accrual.

At the same time, the expected median PFS on observation (Obs) arm is revised in addendum #11 to reflect results from the Spanish SMM trial reported at ASH 2014 (Mateos et al. Blood 2014). In this study, 119 patients were randomized to receive induction lenalidomide (25 mg/day d1-21)-dexamethasone (20 mg/day d1-4, d12-15) (Rd) for 9 cycles and then maintenance lenalidomide (10 mg/day) up to 2 years total treatment versus watchful waiting. Long-term follow-up results showed a survival hazard ratio (watchful waiting/Rd) of 4.35 [95% CI (1.5-13.0)]. Time-to-progression (TTP) hazard ratio was 6.21 [95% CI (3.1-12.7)]. When E3A06 was originally designed, the median progression free survival (PFS) on observation was expected to be 31 months, and it was considered that patients treated with lenalidomide (Revlimid; R) would have comparatively longer PFS (60 months). However, the recent update showed that the median time to progression (TTP) on the watchful waiting arm (akin to the E3A06 observation arm) was 21 months which suggests that the median PFS on the Obs arm might be shorter than we had originally expected. Thus, in this addendum, in addition to the anticipated accrual rate, the expected median PFS on the Obs arm is also revised. The total accrual, the total information time and the interim analysis plan are also amended, accordingly.

Before this amendment (addendum #11), the trial was designed to have 95% power, at the one-sided 0.025 significance level, to reject the null hypothesis of no difference between Obs and R arms, given a true PFS Obs/R hazard ratio of 2.0 or more with 336 patients (accrued over 48 months and followed an additional 6 months) and 124 PFS events. The design incorporated 5 interim analyses and one final analysis for the PFS comparison. No interim analysis has been performed prior to this amendment.

9.2 Accrual

Accrual to E4A03, an ECOG study of newly diagnosed patients looking at treatment with lenalidomide and dexamethasone, reached a rate of 300 patients per year. For every 10 newly diagnosed myeloma patients, the study team feels there are 2 newly diagnosed SMM patients, equating to 60 newly diagnosed SMM patients per year. Of these newly diagnosed SMM patients, approximately 90% fall into intermediate and high risk class based on Kyle's definition which provides for 54 patients per year. Approximately 90% of these have abnormal

Rev. 12/13

Rev. 12/13

Rev. 7/14

free light chain (< 0.26 or > 1.65), however, we will conservatively estimate 65% enrollment. Therefore, the ECOG-ACRIN accrual rate to this study is expected to be 36 patients per year, or 3 patients per month. SWOG and other collaborative groups' contribution to accrual is estimated at 4 patients per month or 48 patients per year. Given an estimated accrual rate of 7 patients per month, we will accrue for 48 months to obtain 336 patients (168 on each arm) for the Phase III study.

Rev. 1/16

Based on observed accrual as of June 2015, the accrual rate is revised to 3-4 patients per month. With a new accrual target of 180 patients and approximately 87 patients remaining to be enrolled, it is anticipated enrollment will be completed in 24 months.

9.3 Phase II Study

Rev. 9/12

A phase II group of patients will be enrolled all receiving lenalidomide at a fixed dose of 25 mg days 1-21 every 28 days to evaluate the early toxicity and tolerance of this dosing. Patients will be treated until progression or excessive toxicity. While all toxicities and dose modifications will be monitored, the primary endpoint for the phase II study will be grade 3 toxicity effecting vital organ function (such as cardiac, hepatic or thromboembolic) or any grade 4 or higher non-hematologic toxicity observed within 6 cycles of treatment. Toxicities evaluated will be based on CTEP-AERS expedited reporting. An acceptable toxicity rate is 15% and a toxicity rate of 30% or greater is considered unacceptable. 34 patients will be enrolled in the phase II cohort. If 9 or more patients experience toxicity as defined then the study will not continue. With this design, the probability of stopping early is 73.2% if the true but unknown toxicity rate is 30%, and 5.9% if the true rate is 15%. Accrual is expected to take approximately 5 months and the toxicity expected to be analyzed approximately 2-3 months after the last patient has completed 6 cycles of treatment.

Rev. 7/14

Thirty-six patients enrolled in the phase II study. Due to an error in the registration system, 8 additional patients were directly assigned to lenalidomide treatment. These 8 patients will be analyzed with the phase II cohort in the final analysis of study results, and in particular will be included in the final adverse event analyses. They may also be included in some correlative analyses. The final phase II cohort thus includes 44 patients.

Rev. 7/13

Rev. 1/16

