2.1 Phase II

2.1.1 Primary Objective

2.1.1.1 To study the risk of grade 3 adverse events that effect vital organ function (such as cardiac, hepatic or thromboembolic) or any grade 4 or higher non-hematologic adverse events among patients receiving lenalidomide as treatment for high-risk asymptomatic, smoldering multiple myeloma.

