5.2.1 Purpose

Adverse event data collection and reporting, which are required as part of every clinical trial, are done to ensure the safety of patients enrolled in the studies as well as those who will enroll in future studies using similar agents. Adverse events are reported in a routine manner at scheduled times during a trial (please refer to the E3A06 Forms Packet for the list of forms with directions for routine adverse event reporting). Additionally, certain adverse events must be reported in an expedited manner for more timely monitoring of patient safety and care. The following sections provide information about expedited reporting.

Rev. 2/12,
7/13

Rev. 7/13

Rev. 7/14
Rev. Add13

Rev. Add13

5.2.2

Determination of reporting requirements

Reporting requirements may include the following considerations: 1) whether the patient has received an investigational or commercial agent; 2) the characteristics of the adverse event including the grade (severity), the relationship to the study therapy (attribution), and the prior experience (expectedness) of the adverse event; 3) the phase (1, 2, or 3) of the trial; and 4) whether or not hospitalization or prolongation of hospitalization was associated with the event.

An investigational agent is a protocol drug administered under an Investigational New Drug Application (IND). In some instances, the investigational agent may be available commercially, but is actually being tested for indications not included in the approved package label.

Steps to determine if an adverse event is to be reported in an expedited manner:

Step 1: *Identify the type of event:* The descriptions and grading scales found in the revised NCI Common Terminology Criteria for Adverse Events (CTCAE) version 4.0 will be utilized until March 31, 2018 for AE reporting. Effective April 1, 2018 all expedited adverse event reporting done via CTEP-AERS will use CTCAE version 5.0 terminology and grading. All appropriate treatment areas should have access to a copy of the CTCAE version 5.0. A copy of the CTCAE version 5.0 can be downloaded from the CTEP website (http://ctep.cancer.gov/protocolDevelopment/electronic_applications/ctc.htm).

Step 2: Grade the event using the NCI CTCAE version 5.0.

Step 3: *Determine whether the adverse event is related to the protocol therapy (investigational or commercial).* Attribution categories are as follows: Unrelated, Unlikely, Possible, Probable, and Definite.

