Unrelated Unlikely	Not Required	Not Required	Not Required	10 Calendar Days	Not Required	10 Calendar Days	Not Required	10 Calendar Days	10 Calendar Days
Possible Probable Definite	Not Required	10 Calendar Days	Not Required	10 Calendar Days	10 Calendar Days	10 Calendar Days	Not Required	24-Hour; 5 Calendar Days	10 Calendar Days

¹ Adverse events with attribution of possible, probable, or definite that occur **greater** than 30 days after the last dose of treatment with an agent under a CTEP IND require reporting as follows:
 CTEP-AERS 24-hour notification followed by complete report within 5 calendar days for:
 • Grade 4 and Grade 5 unexpected events
 CTEP-AERS 10 calendar day report:
 • Grade 3 unexpected events with hospitalization or prolongation of hospitalization
 • Grade 5 expected events

² Although a CTEP-AERS 24-hour notification is not required for death clearly related to progressive disease, a full report is required as outlined in the table. See NOTE below regarding how to report a death due to progressive disease.
 Please see additional information below under section entitled “Additional instructions, requirements, and exceptions for protocol E3A06”

March 2005

NOTE: All deaths on study or within 30 days of the last dose of treatment require both routine and expedited reporting regardless of causality. Attribution to treatment or other cause should be provided.

NOTE: A death due to progressive disease should be reported as a Grade 5 “Disease progression” under the System Organ Class (SOC) “General disorder and administration site conditions”. Evidence that the death was a manifestation of underlying disease (e.g. radiological changes suggesting tumor growth or progression: clinical deterioration associated with a disease process) should be submitted.

NOTE: A death that occurs > 30 days after the last dose of treatment and is attributed possibly, probably, or definitely to the treatment must be reported within 10 calendar days of learning of the event.

- Expedited AE reporting timelines:
 - **24 Hours; 5 calendar days** – The investigator must initially report the AE via CTEP-AERS within 24 hours of learning of the event followed by a complete CTEP-AERS report within 5 calendar days of the initial 24-hour report.
 - **10 calendar days** – A complete CTEP-AERS report on the AE must be submitted within 10 calendar days of the investigator learning of the event.

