- Any medical event equivalent to CTCAE grade 3, 4, or 5 that precipitates **hospitalization* (or prolongation of existing hospitalization)** must be reported regardless of attribution and designation as expected or unexpected

with the exception of any events identified as protocol-specific expedited adverse event reporting exclusions.

- Any event that results in **persistent or significant disability/incapacity, congenital anomaly, or birth defect** must be reported via CTEP-AERS if the event occurs following treatment with an agent under a CTEP IND.
- Use the NCI protocol number and the protocol-specific patient ID provided during trial registration on all reports.

*Hospitalizations are defined as lasting 24 hours or longer and these events must be reported via CTEP-AERS.

Additional instructions, requirements and exceptions for protocol E3A06

1. Additional Instructions:

- With respect to determining the specific day by which the event must be reported, the day the reporter learns of the adverse event constitutes “Day 0”
- For instructions on how to specifically report events that result in persistent or significant disability/incapacity, congenital anomaly, or birth defect events via CTEP-AERS, please contact the AEMD Help Desk at [contact] or [contact]. This will need to be discussed on a case-by-case basis.

2. ECOG-ACRIN and Protocol Specific expedited reporting requirements:

The adverse events listed below also require expedited reporting for this trial:

ECOG-ACRIN specific expedited reporting requirements:

- **Hospitalizations:** Any grade 1 or 2 adverse event with precipitates a hospitalization lasting ≥ 24 hours (or prolongs hospitalization) must be reported via CTEP-AERS within 10 calendar days of learning of the event regardless of the attribution and designation as expected or unexpected.
- **Grade 3 expected events:** Any grade 3 expected **non-hematologic** event, with an attribution of possible, probable of definite, must be reported via CTEP-AERS within 10 calendar days of learning of the event, regardless of whether hospitalization is required.

➤ **Pregnancies**

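### Section 9.3 counts the Phase II primary toxicity endpoint from expedited reports, which do not require non-hospitalised grade 3 events judged unrelated or unlikely, so the reported rate can be understated

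*Combined protocol and SAP*

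**What the plan says.** Objective 2.1.1.1 is "To study the risk of grade 3 adverse events that effect vital organ function", together with any non-hematologic event of grade 4 or higher. Section 9.3 turns this into the endpoint: "the primary endpoint for the phase II study will be grade 3 toxicity effecting vital organ function (such as cardiac, hepatic or thromboembolic"), again with grade 4 or higher non-hematologic toxicity, over 6 cycles. Neither text mentions attribution or hospitalisation.

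Section 9.3 then names the data source: "Toxicities evaluated will be based on CTEP-AERS expedited reporting". The rule stops the study at 9 or more affected patients out of 34. The stated probability of stopping is 73.2% at a true rate of 30% and 5.9% at 15%. Thirty-six patients enrolled, 8 more were assigned lenalidomide directly through a registration error, and the final Phase II cohort is 44.

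The table in section 5.2.6 decides which events reach CTEP-AERS. Its first attribution row begins "Unrelated Unlikely Not Required Not Required Not Required 10 Calendar Days Not Required 10 Calendar Days". The fourth to sixth entries are grade 3 unexpected with hospitalisation, grade 3 unexpected without it, and grade 3 expected with it. The next entry, grade 3 expected without hospitalisation, is also not required. An ECOG-ACRIN addition in the same section brings in grade 3 expected non-hematologic events, but only those "with an attribution of possible, probable of definite, must be reported via CTEP-AERS within 10 calendar days".

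There is a second data stream. Section 5.2.1 says: "Adverse events are reported in a routine manner at scheduled times during a trial". Section 9.3 does not name it as a source for the endpoint.

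**The concern.** The endpoint definition and its data source do not cover the same events. The definition is silent on attribution. The source applies an attribution filter to one part of the endpoint, grade 3 events without hospitalisation. A grade 3 hepatic or thromboembolic event managed as an outpatient and called unlikely by the site fits the definition, but no expedited report is required for it.

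Phase II has a single arm, so there is no control rate against which to judge site attribution. Letting attribution decide whether a vital-organ event counts weakens a primary safety endpoint. Against the endpoint as worded, any error from this gap goes one way, towards fewer affected patients and a lower chance of meeting the stopping rule.

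**Working it through.** **Step 1: which parts of the endpoint must be reported.** For events on treatment or within 30 days of the last dose, section 5.2.6 gives:

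| Endpoint event | Attribution | Hospitalised | CTEP-AERS report |
|---|---|---|---|
| Grade 3, unexpected | possible to definite | yes or no | required (table) |
| Grade 3, expected | possible to definite | yes | required (table) |
| Grade 3, expected, non-hematologic | possible to definite | no | required (ECOG-ACRIN addition) |
| Grade 3 | unrelated or unlikely | yes | required (table) |
| **Grade 3** | **unrelated or unlikely** | **no** | **not required** |
| Grade 4 or 5, non-hematologic | any | yes or no | required (table) |

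The protocol-specific exception in 5.2.6 covers only grade 4 expected myelosuppression. That is hematologic and so outside the endpoint. The gap is one combination, and no other rule in 5.2.6 fills it.

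**Step 2: reproduce the plan's figures.** Inputs from section 9.3: n = 34, threshold 9, true rates 30% and 15%. With X the number of affected patients, P(stop) = P(X ≥ 9), X ~ Binomial(34, p).

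- p = 0.30: 0.7323 (stated 73.2%)
- p = 0.15: 0.0587 (stated 5.9%)

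Both reproduce. Both take p as the rate that is actually counted, so they assume full capture.

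**Step 3: effect of incomplete capture.** Let c be the share of affected patients with at least one event that must be reported. The counted rate is c × p. The documents give no value for c, so the values below are assumptions.

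| Share missed (1 − c) | Counted rate, true 30% | P(stop) | Counted rate, true 15% | P(stop) |
|---|---|---|---|---|
| 0 | 30% | 73.2% | 15% | 5.9% |
| 5% | 28.5% | 66.6% | 14.25% | 4.4% |
| 10% | 27% | 59.2% | 13.5% | 3.3% |
| 20% | 24% | 43.2% | 12% | 1.6% |
| 30% | 21% | 27.4% | 10.5% | 0.7% |

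At a true 30% rate, 0.30 × 34 = 10.2 affected patients are expected. A 10% loss is 0.10 × 10.2 ≈ 1 patient. On average, one uncounted patient lowers the chance of stopping by 73.2 − 59.2 = 14.0 percentage points.

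With the 36 patients who enrolled and the same threshold of 9, P(stop) at 30% is 79.6% with full capture, 73.7% with a 5% loss and 66.8% with a 10% loss.

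**Step 4: effect on the final result.** On the final cohort of 44, each affected patient left out lowers the reported rate by 1/44 = 2.3 percentage points.

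**The case against.** **Toxicity may mean treatment-related.** Section 9.3 says toxicity where the objective says adverse events, and section 5.4 ties dose modification to drug-related events. On that reading the omitted events do not belong in the count. The expedited stream could even over-count, because it takes grade 4 and 5 events and hospitalised grade 3 events whatever their cause. Two things weigh against this defence. Section 9.5 compares toxicities across all randomized patients, including an observation arm that receives no drug. Section 5.4 states its attribution limit in words, and section 9.3 has none. The stream also matches neither reading: it ignores attribution at grade 4 and above and depends on it for outpatient grade 3 events. What stands is that section 9.3 does not say outright which reading is meant.

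**The decision is past.** This stands. Section 9.1 dates the start of Phase III accrual to February 2013, and under the Schema the randomized part follows the Phase II safety analysis. Step 3 describes how the rule behaves. It does not show that the decision was wrong, although a reader might infer that.

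**The size has no anchor.** This also stands. A patient is lost only if every qualifying event falls in the one gap, and the documents show no such event. Nor do they show which version of the reporting table governed the Phase II cohort. A reader might conclude that the rate is understated; the documents support only that it can be.

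**Other safety review is wider.** Correct. Section 9.3 says all toxicities are monitored, section 9.5 has adverse events monitored on all patients, and section 9.10 gives the monitoring committee regular safety reviews. Section 9.3 does not say that the final analyses use expedited reports alone, but it names no other source for the primary endpoint.

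**Two further readings go too far.** A reader might add events occurring more than 30 days after an early stop, when only related events must be reported. That requires a 24-week calendar window, and section 9.3 counts cycles of treatment. A reader might also think that related grade 3 thromboembolic events are lost because section 5.3 lists them as exceptions to expedited reporting. The ECOG-ACRIN addition in 5.2.6 requires them.

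**Conclusion.** The mismatch holds. As worded, the endpoint covers events of any attribution, while its stated source need not contain non-hospitalised grade 3 events judged unrelated or unlikely. The reported Phase II rate can therefore be understated, and the 73.2% is correct only with full capture: illustratively 66.6% or 59.2% if 5% or 10% of affected patients are missed. These figures rest on an assumed loss rate and on reading the endpoint as all-cause, which the wording of 2.1.1.1 and 9.3 supports. The live consequence is the final Phase II toxicity result, a primary endpoint. The correction is worth making because it is cheap and takes site attribution out of that result.

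**What to change.** In section 9.3, for the final Phase II report, replace the data-source sentence with text such as: *For the final Phase II report, the endpoint is counted from routinely collected adverse event data, supplemented by CTEP-AERS reports, irrespective of attribution or hospitalisation. Treatment-related events are also tabulated separately.* Keep the six-cycle window as now written, and apply the count to the final cohort of 44. The stopping rule needs no change, since it has already been used.

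The cost is wording, a re-count, and a reported toxicity rate that may be somewhat higher. The re-count assumes that the routine forms record these events with grade and attribution. Their content is in the Forms Packet, which is not among the documents, so this should be checked first.
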